10.5.2.2 Safety Variables and Monitoring

10.5.2.2.1 Definitions

Definitions and classifications for specific adverse events to be reported from this study will conform, as much as practicable, with those in draft development or finalized by the Brighton Collaboration (http://brightoncollaboration.org).

- An *adverse event* (AE) is defined as any untoward medical occurrence in a clinical investigation subject administered a pharmaceutical product, at any dose, or placebo. It does not necessarily require a causal relationship with this treatment. An AE can therefore be any unfavorable and unintended sign (including abnormal laboratory findings), symptom, or disease temporally associated with the use of a medicinal product, whether or not considered related to the medicinal product. This definition includes intercurrent illnesses or injuries, and exacerbation of pre-existing conditions.
- An *expected* AE is one previously known or anticipated as a result of (a) the interventions and interactions used in the research, (b) the collection of identifiable private information for the research; (c) an underlying disease, disorder, or condition of the human subject; and/or (d) other circumstances unrelated to the research or any underlying disease, disorder, or condition of the subject.
- An *unanticipated* AE is an unexpected occurrence or frequency of a type not previously known or commonly identified to result from (a) the

HIRRC/CDC Needle-free Intradermal	Page 80	File: 4785-ID-INF-Prot-Engl-2008Jun24.doc
Influenza Study - CDC-ISO-4785	of 138	2008-Jun-24

interventions and interactions used in the research; (b) the collection of identifiable private information under the research; (c) an underlying disease, disorder, or condition of the human subject; and/or (d) other circumstances unrelated to the research or to any underlying disease, disorder, or condition of the subject.

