10.5.2.2.3 Seriousness

A *Serious Adverse Event* is defined as any untoward medical occurrence which...:

- Results in death.
- Is life threatening (i.e., the subject was, in the opinion of the investigator, at immediate risk of death from the event as it occurred).
- Requires or prolongs inpatient hospitalization.
- Results in persistent or significant disability or incapacity, (i.e., the event causes a substantial disruption of a person's ability to conduct normal life functions).
- Is a congenital anomaly or birth defect.
- Is an important and significant medical event that, based upon appropriate medical judgment, may jeopardize the subject and may require

HIRRC/CDC Needle-free Intradermal	Page 81	File: 4785-ID-INF-Prot-Engl-2008Jun24.doc
Influenza Study - CDC-ISO-4785	of 138	2008-Jun-24

medical or surgical intervention to prevent one of the other outcomes defining serious. $\frac{1}{2}$

1. Medical and scientific judgment should be exercised in deciding whether an adverse event not satisfying any of the first five bullets above is "important and significant" and thus should be classified as a Serious Adverse Event (SAE) and reported by expedited method. Examples of such events that would usually be considered important and significant include (a) allergic bronchospasm requiring intensive treatment in an emergency room or at home, (b) bleeding disorders or (c) convulsions that may not result in inpatient hospitalization, (d) the development of drug dependency or drug abuse, or (e) a diagnosis of cancer. Examples of medical events that would usually NOT be considered SAEs, if deemed unrelated to the vaccine, which resolve upon standard treatment with drugs or other therapies, and which do not result in any of the outcomes described in the first five bullets of the SAE definition above, would usually include common acute childhood conditions such as (f) otitis media, (g) upper respiratory infection, (h) influenza and similar illness, (i) mild reactive airway disease or asthma, (j) diarrhea, (k) impetigo, and (l) intestinal parasitosis. All such events not considered SAEs would still be reported routinely as adverse events (AEs) on the Case Report Form.

It should be noted that a *severe* Adverse Event need not be *serious* in nature and that a *serious* Adverse Event need not, by definition, be *severe*.

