10.9.2 Phase II

In accordance with the same criteria and procedures as described for Phase I in section 10.9.1 above, in phase II (n=402), all vaccination shall be suspended, upon the occurrence of *possibly-related* or *probably-related Serious Adverse Events* in sixteen (16 [4%]) or more vaccinees, or *possibly-related* or *probably-related entire-limb swelling* or other *severe local reactions* at the INF injection site in twenty (20 [5%]) or more vaccinees.

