10.10 Criteria for Proceeding to Phase II

Upon unblinded analysis by the DSMB (see section 10.11) of the results of the phase I study, the observed adverse reactions will be tallied by the DSMB for each of the study arms (control IM-NS-0.25, investigational IM-NS-0.1 and ID-JI-0.1). Either or both investigational study arm(s) for which an observed numbers of reactions exceeds the number observed in the IM-NS-0.25 control arm by the following degree for any reactions listed will be eliminated from the phase II study. If both investigational arms are thus eliminated, the study will not proceed to phase II.

	Excess = no. in investigational arm less no. in control arm
Serious Adverse Reaction, possibly- or probably-related	≥3
Fever >40° C, possibly- or probably-related	≥4
Injection site whole-limb swelling	≥4

HIRRC/CDC Needle-free Intradermal	Page 103	File: 4785-ID-INF-Prot-Engl-2008Jun24.doc
Influenza Study - CDC-ISO-4785	of 138	2008-Jun-24

Injection site induration >5 cm in diameter	≥5
Injection site erythema >5 cm in diameter	≥5
Injection site pain level 3 (cries upon moving limb)	≥5

For example, if four (4) children in the IM-NS-0.25 control arm experience inducation of >5 cm, eight (8) do so from the IM-NS-0.1 arm, and nine (9) from the ID-JI-0.1 arm, then the IM-NS-0.1 study arm may proceed to phase II, but the ID-JI-0.1 arm will be dropped from phase II.

Based upon this analysis and any other relevant information, the DSMB will decide whether or not the study should proceed to phase II as designed, should be modified and then proceed, or should be terminated. This decision shall be duly informed to the investigators, without revealing unblinded information nor study-group-specific analyses. Regardless of a DSMB decision permitting phase II, the study sponsor may elect for any reason not to proceed, and to terminate the study after phase I.

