10.11 Data and Safety Monitoring Board

A Data and Safety Monitoring Board (DSMB) will be appointed in advance of the study (see section 8.8). Its members will certify no financial or related interests in any of the organizations conducting or cooperating with the study: CDC, HIRRC, WHO, PATH, or Bioject. Any disclosed exceptions to the certification shall be considered by the DSMB prior to material discussions so that they may be reflected in the minutes along with the DSMB's determination how to handle such exceptions. The group expertise will include the fields of vaccine science, immunization, pediatrics, public health, statistics, and clinical medical research. Statistical expertise will be provided by [name], DSMB Chair, who will be assisted, as needed, by fellow faculty and programmers of the Johns Hopkins University School of Public Health.

In advance of implementation of the study, members of the DSMB will each be provided with drafts of key study documents (protocol, consent form, case report form, diary forms, etc.) for an opportunity to review them and suggest changes on the basis of their scientific expertise and personal experience. One or more of the DSMB members will assist in preparing the allocation cards and envelopes used to randomize consecutive participant ID numbers into the three study arms. During the blinded period of the trial the DSMB will maintain in at least three separate locations the coding list to identify these allocations by study ID number.

The DSMB shall meet formally by telephone conference call at least four times: (1) prior to initiation of the study, (2) during the phase I enrollment period, (3) upon being provided with blinded clinical data from the completion of the phase I clinical aspects, and (3) upon being provided with unblinded analysis following the completion of clinical and laboratory analysis from phase II. In addition, the DSMB may meet for any requested *ad hoc* meetings as described above, or upon its own initiative for cause.

HIRRC/CDC Needle-free Intradermal	Page 104	File: 4785-ID-INF-Prot-Engl-2008Jun24.doc
Influenza Study - CDC-ISO-4785	of 138	2008-Jun-24

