10.12 Early Reporting to DSMB and IRBs

The conjunction of certain adverse events (AEs) and unanticipated problems will be reported promptly as they occur to the DSMB and both IRBs (see definitions for terms in section 10.5.2.2) These shall include:

- Any *serious* AE (SAE) that is also an *unanticipated* AE, and is *probably-related* or *possibly-related* to participation in the research.
- A series of *serious* AEs that are expected in some participants, but in the judgment of the investigators are occurring at a significantly higher frequency or severity than expected.
- Certain *unanticipated* AEs, regardless of severity, that might alter the IRB's analysis of the risk versus potential benefit of the research *and*, as a result, might warrant substantive changes in the research protocol such as the informed consent process and form, exclusion criteria, monitoring methods, or termination of enrollment.
- *Unanticipated problems that do not involve adverse events*, but which may have increased the risk of past or future harm to participants

In the event of any such occurrences, the Dominican investigators will document the situation in writing and notify promptly by telephone, fax, or email both the FDI IRB and the U.S. investigators, who shall notify the CDC IRB and the DSMB members, and at their discretion, the vaccine and jet injector manufacturers.

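### Related fever above 40 °C can eliminate an arm after phase I but has no counted safety review in phase II

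*Protocol*

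**What the plan says.** Section 10.10 tallies reactions by arm once, at the end of phase I. It gives "Fever >40° C, possibly- or probably-related" a line separate from serious adverse events. An excess of 4 or more children over control on that line alone removes the arm. The same section adds: "Based upon this analysis and any other relevant information, the DSMB will decide" whether phase II proceeds, is modified or is dropped.

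Section 10.9.2 governs phase II (n=402). Vaccination stops for related serious adverse events in 16 or more vaccinees (4%), or for related entire-limb swelling or other severe local reactions "at the INF injection site in twenty (20 [5%]) or more vaccinees". The synopsis repeats these two classes. Section 10.9.1 uses the same two classes in phase I and has no fever item either.

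Other routes to the DSMB:
- **10.5.2.2.3 (seriousness).** There is no temperature criterion. An event may still qualify if it "Is an important and significant medical event that, based upon appropriate medical judgment, may jeopardize the subject", and convulsions are given as an example.
- **10.12 (early reporting).** It covers certain unanticipated events, "regardless of severity, that might alter" the ethics boards' view of risk against benefit. Under 10.5.2.2.1 such an event "is an unexpected occurrence or frequency of a type not previously known or commonly identified to result from" the research, so an unusual frequency can qualify.
- **10.11 (meetings).** After the end-of-phase-I review, the next formal meeting comes "upon being provided with unblinded analysis following the completion of clinical and laboratory analysis from phase II". Ad hoc meetings may be held on request "or upon its own initiative for cause".

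Section 12.1 tells readers that the stopping rules are conservative and allow a fast response to any clinical outcome pointing to undue risk.

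**The concern.** The sponsor singles out high fever as a reaction that can end an arm, but applies the check once, to 48 children. The other 402 are vaccinated under a rule that does not count it. Investigators and assessing staff are blinded (10.4.6), so they see a pooled number and must decide, with no stated threshold, whether it is unusual. An excess confined to one arm could build up through phase II without the DSMB being required to look at fever by arm until vaccination is over.

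**Working it through.** **1. The plan's own percentages.** 16/402 = 3.98% and 20/402 = 4.98%, matching the stated 4% and 5%. Phase I: 3/48 = 6.25% and 5/48 = 10.4%, matching 6% and 10%. Phase II share: 402/450 = 89%.

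**2. Each 10.10 item set against 10.9.2.**

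| 10.10 item | Excess that removes an arm | Counterpart in 10.9.2 |
|---|---|---|
| Related serious adverse reaction | ≥3 | Related serious adverse events, ≥16 |
| Related fever >40 °C | ≥4 | None |
| Whole-limb swelling | ≥4 | Entire-limb swelling or other severe local reactions, ≥20 |
| Induration >5 cm, erythema >5 cm, pain level 3 | ≥5 each | Same local-reaction count, if graded severe |

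**3. Size of the 10.10 fever criterion.** 4/16 = 25 percentage points. The same excess in a phase II arm is 0.25 × 134 = 33.5, about 34 children. If none of them met the serious-event definition, neither 10.9.2 count would move.

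**4. What that criterion catches in phase I.** With X ~ Bin(16, p) in one investigational arm and Y ~ Bin(16, c) in control, P(X − Y ≥ 4) is 0.005 to 0.007 at p = 5%, and 0.053 to 0.064 at p = 10%, for c from 0.5% to 2.1%. A moderate excess would nearly always pass into phase II.

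**5. Background rate (assumption).** The protocol gives no rate for fever above 40 °C. Section 10.4.2.6 reports 2.1% severe fever at 6 to 36 months without a cut-off. I use 0.5% to 2.1% per child: 134 × 0.005 = 0.7 to 134 × 0.021 = 2.8 per arm, and 2.0 to 8.4 among 402. The arm rates of 5%, 10% and 15% are illustrations.

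**6. A pooled prompt at 16 of 402.** P(A + B ≥ 16), with A ~ Bin(134, p) in one arm and B ~ Bin(268, c) in the other two, by exact convolution:

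| Background c | No excess | One arm 5% | One arm 10% | One arm 15% |
|---|---|---|---|---|
| 0.5% | <0.001 | 0.007 | 0.40 | 0.92 |
| 1% | <0.001 | 0.03 | 0.55 | 0.96 |
| 2.1% | 0.012 | 0.18 | 0.80 | 0.99 |

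**7. Lower counts.** At a 2.1% background, a count of 14 fires 0.047 of the time with no excess and 0.35 with one arm at 5%. A count of 10 suits a 1% background (0.008 with no excess, 0.46 with one arm at 5%) but fires 0.34 of the time with no excess if the background is really 2.1%.

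**The case against.** The strongest reply is that the two rules do different jobs. Section 10.10 is a single unblinded comparison between arms. Section 10.9 is an automatic halt on pooled counts, and nothing says it must mirror 10.10. Fever is an expected reaction at this age, so keeping it out of an automatic halt is defensible. That stands, and the fix below does not halt vaccination.

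A reader might infer that 10.9 and 10.10 contradict each other, or that any related fever above 40 °C is enough to drop an arm. The documents support neither. Section 10.10 needs an excess of 4 over control in arms of 16, and step 4 shows that arms at 5% or 10% would seldom meet it.

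A reader might also infer that high fever in phase II goes unmonitored. It does not. Temperatures are recorded daily on days 0 to 7 (10.5.2.1), a related high fever may be judged serious, an unanticipated frequency must be reported under 10.12, and the DSMB can meet ad hoc. An extra 34 fevers in one arm would be hard to overlook even in pooled data. But none of these routes carries a number, and they are weakest for excesses short of that size.

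Finally, 10.10 already lets the DSMB have the study modified before phase II, so it could add a fever count itself. This permits the remedy but does not require it.

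**Conclusion.** The point holds as a gap in coverage. Related fever above 40 °C is the only 10.10 item that 10.9.2 does not count, and no formal DSMB meeting falls within phase II vaccination. For fevers that are not serious adverse events, DSMB review depends on judgement exercised on blinded, pooled data, which is less than 12.1 promises. It is worth considering rather than essential, because the discretionary routes are real and the most extreme excess would probably be noticed.

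The textual finding needs no assumed rate. The operating figures rest on the assumed 0.5% to 2.1% background, the illustrative arm rates and 134 children per arm. Possibly related events include those equally explained by another cause (10.5.2.2.4), so ordinary febrile illness could push the true background higher and make the prompt fire more often.

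**What to change.** Add one sentence to 10.9.2 and one to the phase II stopping rules in the synopsis: when possibly or probably related fever above 40 °C has occurred in 16 (4%) or more phase II vaccinees, the data go promptly to the DSMB for unblinded review by arm, without automatic suspension. Sixteen is the count that 10.9.2 already uses for serious adverse events. Let the DSMB lower it before phase II once it has seen the phase I fevers. Section 10.9.1 needs no change, because phase I fevers already face the by-arm comparison in 10.10.

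The change uses temperatures already collected and a board that already holds the codes. The cost is an occasional extra ad hoc review: probability about 0.01 with no excess at a 2.1% background, near 0 at 1% or less, and more if the DSMB picks a count too low for the true background. The sentence should call this a safety prompt and not a test, since it finds large excesses well and modest ones poorly.

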10.10 Criteria for Proceeding to Phase II

Upon unblinded analysis by the DSMB (see section 10.11) of the results of the phase I study, the observed adverse reactions will be tallied by the DSMB for each of the study arms (control IM-NS-0.25, investigational IM-NS-0.1 and ID-JI-0.1). Either or both investigational study arm(s) for which an observed numbers of reactions exceeds the number observed in the IM-NS-0.25 control arm by the following degree for any reactions listed will be eliminated from the phase II study. If both investigational arms are thus eliminated, the study will not proceed to phase II.

	Excess = no. in investigational arm less no. in control arm
Serious Adverse Reaction, possibly- or probably-related	≥3
Fever >40° C, possibly- or probably-related	≥4
Injection site whole-limb swelling	≥4

HIRRC/CDC Needle-free Intradermal	Page 103	File: 4785-ID-INF-Prot-Engl-2008Jun24.doc
Influenza Study - CDC-ISO-4785	of 138	2008-Jun-24

Injection site induration >5 cm in diameter	≥5
Injection site erythema >5 cm in diameter	≥5
Injection site pain level 3 (cries upon moving limb)	≥5

For example, if four (4) children in the IM-NS-0.25 control arm experience inducation of >5 cm, eight (8) do so from the IM-NS-0.1 arm, and nine (9) from the ID-JI-0.1 arm, then the IM-NS-0.1 study arm may proceed to phase II, but the ID-JI-0.1 arm will be dropped from phase II.

Based upon this analysis and any other relevant information, the DSMB will decide whether or not the study should proceed to phase II as designed, should be modified and then proceed, or should be terminated. This decision shall be duly informed to the investigators, without revealing unblinded information nor study-group-specific analyses. Regardless of a DSMB decision permitting phase II, the study sponsor may elect for any reason not to proceed, and to terminate the study after phase I.

10.11 Data and Safety Monitoring Board

A Data and Safety Monitoring Board (DSMB) will be appointed in advance of the study (see section 8.8). Its members will certify no financial or related interests in any of the organizations conducting or cooperating with the study: CDC, HIRRC, WHO, PATH, or Bioject. Any disclosed exceptions to the certification shall be considered by the DSMB prior to material discussions so that they may be reflected in the minutes along with the DSMB's determination how to handle such exceptions. The group expertise will include the fields of vaccine science, immunization, pediatrics, public health, statistics, and clinical medical research. Statistical expertise will be provided by [name], DSMB Chair, who will be assisted, as needed, by fellow faculty and programmers of the Johns Hopkins University School of Public Health.

In advance of implementation of the study, members of the DSMB will each be provided with drafts of key study documents (protocol, consent form, case report form, diary forms, etc.) for an opportunity to review them and suggest changes on the basis of their scientific expertise and personal experience. One or more of the DSMB members will assist in preparing the allocation cards and envelopes used to randomize consecutive participant ID numbers into the three study arms. During the blinded period of the trial the DSMB will maintain in at least three separate locations the coding list to identify these allocations by study ID number.

The DSMB shall meet formally by telephone conference call at least four times: (1) prior to initiation of the study, (2) during the phase I enrollment period, (3) upon being provided with blinded clinical data from the completion of the phase I clinical aspects, and (3) upon being provided with unblinded analysis following the completion of clinical and laboratory analysis from phase II. In addition, the DSMB may meet for any requested *ad hoc* meetings as described above, or upon its own initiative for cause.

HIRRC/CDC Needle-free Intradermal	Page 104	File: 4785-ID-INF-Prot-Engl-2008Jun24.doc
Influenza Study - CDC-ISO-4785	of 138	2008-Jun-24

Upon the incidence of SAEs which trigger the criteria for suspending vaccination, as per section 10.9, the DSMB will analyze the situation in unblinded fashion using the coding sheets, and make its recommendation to the investigators whether or not vaccination may resume or whether the study -- or one of its investigational study arms -- should be terminated.

At the conclusion of phase I, the DSMB will be provided by the investigators with adverse events and other results from the phase, linked to study ID number. As per section 10.10, the DSMB will link this data with the study allocation group information from the coding sheets and analyze them for purposes of applying the rules for proceeding to phase II, and so inform the investigators of their conclusions.

Upon the completion of the blinded clinical and serologic aspects of the study, after either a termination following phase I or upon completion of phase II, upon request the DSMB will furnish the investigators the coding lists so that unblinded analysis of the results may occur.

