Serum and Virus Collection (§10.6.10): Blood specimens to measure serologic responses will be collected three times, just prior to vaccination on day 0 (INF dose 1), on day 28 (INF dose 2), and on day 56 (INF "insurance" dose 3). Participants with influenza-like illness will have nasopharyngeal/throat swabs analyzed by rapid influenza test. Those with positive influenza A results will have specimens sent for viral culture.

Stopping rules (§10.9): Vaccination will be suspended for all participants, pending unblinded review by the DSMB and its clearance or denial to resume, as well as simultaneous IRB guidance, upon occurrences deemed *possibly-* or *probably-related* to the study vaccinations by any of the Dominican or U.S. Principal or Senior Investigators of *serious adverse events* in any 3 (6%) phase I vaccinees or any 16 (4%) phase II vaccinees, or upon incidents of *entire-limb swelling* or other *severe local reactions* at the **INF** injection site in any 5 (10%) phase I vaccinees or any 20 (5%) phase II vaccinees.

Criteria for proceeding to phase II (§10.10): Either or both of the study's investigational arms (**ID-JI-0.1** or **IM-NS-0.1**) will not proceed to phase II if the observed frequency of the following events in that arm exceeds the frequency observed in the control **IM-NS-0.25** group by the designated excess: (Invest. Arm) – (Control Arm)

-	· · · · · · · · · · · · · · · · · · ·	
•	Any serious adverse event, possibly- or probably-related:	exceeds by ≥ 3
•	Fever >40° C possibly- or probably-related:	exceeds by ≥4
•	Injection site whole-limb swelling:	exceeds by ≥4
•	Injection site induration >5 cm diameter:	exceeds by ≥ 5
•	Injection site erythema >5 cm diameter:	exceeds by ≥ 5
•	Injection site pain level 3 (cries upon moving limb):	exceeds by ≥ 5

Number of participants planned:

Phase I = 48; phase II = 402 (total participants = 450)

Participant characteristics and main criteria for inclusion and exclusion (§10.3):

Healthy, full-term infants of age ≥ 6 -to- <24 months (before second birthday) who are recruited as prior or current patients, or siblings of patients, attending a public outpatient clinic at the national children's hospital. Excluded will be infants not up-to-date on immunizations who need other injected vaccines recommended routinely at younger ages, or

HIRRC/CDC Needle-free Intradermal	Page 6	File: 4785-ID-INF-Prot-Engl-2008Jun24.doc
Influenza Study - CDC-ISO-4785	of 138	2008-Jun-24

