The investigational spacer to be studied in this trial has already been subjected to a number of well-conducted studies on adults without serious adverse consequences (see section 10.4.3.6). Thus, it is reasonable now to study young children in order to gather essential data for policymaking on how such participants may be protected in the event of pandemic. This study is phased with conservative stopping rules that can quickly respond to any clinical outcomes suggesting untoward risks to these children.

12.2 Why is this study being done in the Dominican Republic and not in the United States or Europe, where its sponsor and principal parties are based?

This kind of study could and should very well be conducted in the U.S. or Europe, as the questions it poses are relevant to those geographic areas as well. However, the collaboration supporting this study benefits from the technical scientific and/or financial contributions of WHO and PATH, organizations with primary missions to seek answers to the health problems of the developing world. This global perspective is also within the mission of CDC, which recognizes that national health and security depends on the health and security of all nations. The selection of the HIRRC as a partner in this study resulted from its excellent track record of clinical trials of vaccines and antimicrobials (see section 10.2.1).

HIRRC/CDC Needle-free Intradermal	Page 112	File: 4785-ID-INF-Prot-Engl-2008Jun24.doc
Influenza Study - CDC-ISO-4785	of 138	2008-Jun-24

12.3 Why is the study planning to use Vaxigrip[®] instead of an influenza vaccine licensed in the U.S.A.?

The brand of influenza vaccine to use in this study was selected by a process of elimination from among the seven major products on the international market, of which three are now sold in the U.S.

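### No DSMB review is scheduled while phase II children are being vaccinated, and the pooled phase II triggers need not reveal an excess of expected, non-serious reactions in the jet-injector arm

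*Protocol*

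**What the plan says.** **Meetings.** Section 10.11 requires at least four formal DSMB conference calls: before the study, during phase I enrolment, on completion of the phase I clinical work, and "and (3) upon being provided with unblinded analysis following the completion of clinical and laboratory analysis from phase II". Further meetings may be held on request or on the board's own initiative for cause.

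**Data flow.** At the end of phase I, "the DSMB will be provided by the investigators with adverse events and other results from the phase, linked to study ID number". The board then joins these data to the allocation codes it holds. Section 10.11 requires no such transfer during phase II.

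**By-arm rule.** Section 10.10 compares each investigational arm with control once, on phase I results. One of its six criteria is "Fever >40° C, possibly- or probably-related", with an excess of 4 or more eliminating the arm.

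**Phase II triggers.** Section 10.9.2 suspends vaccination at 16 or more vaccinees with related serious adverse events, or when related entire-limb swelling or other severe local reactions occur "at the INF injection site in twenty (20 [5%]) or more vaccinees". The synopsis gives the local-reaction limits as "any 5 (10%) phase I vaccinees or any 20 (5%) phase II vaccinees". Neither place has a per-arm count, and neither lists fever.

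**Early reporting.** Section 10.12 sends the DSMB unanticipated related serious events, series of serious events that "in the judgment of the investigators are occurring at a significantly higher frequency or severity than expected", and certain unanticipated events of any severity. Section 10.5.2.2.1 defines an unanticipated event as "an unexpected occurrence or frequency of a type not previously known or commonly identified to result from" the research or other listed causes.

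**Assurance given.** Section 12.1, defending the choice of this age group, describes the study as "phased with conservative stopping rules that can quickly respond to any clinical outcomes suggesting untoward risks to these children".

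**The concern.** The safety of the jet-injected intradermal arm is research question 2 in section 9.6.4, and section 9.6.2 says there are no earlier data on this route by jet injector at this age. The risk of interest sits in one arm of three. A pooled count dilutes that arm with two others, and a fever that could eliminate an arm after phase I has no numeric consequence in phase II unless it is serious. Size-based criteria such as erythema over 5 cm may also fall outside the phase II count, because section 10.5.2.2.2 grades severity by interference with daily activity.

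If a moderate excess exists, phase I is too small to show it reliably and phase II is where it would appear. By the next scheduled review every phase II child would already have been vaccinated, so the promise of a quick response in 12.1 would not have been kept for that kind of reaction.

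**Working it through.** **1. Are the triggers pooled?** 16/402 = 3.98% and 20/402 = 4.98%, matching the printed 4% and 5%. In phase I, 3/48 = 6.25% and 5/48 = 10.4%, matching 6% and 10%. The percentages reproduce only with all three arms in the denominator. If every event fell in one arm of 134, suspension would need 16/134 = 11.9% (serious) or 20/134 = 14.9% (local).

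**2. Boundary case.** 19 severe local reactions of 134 in the jet arm against 0 of 134 in control, with none in the third arm, does not suspend vaccination. One-sided Fisher p = 9.6 × 10⁻⁷.

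**3. Inputs for the illustration.**
- Arm sizes: 16 (phase I) and 134 (phase II), from section 10.1.2.
- Background rates, from section 10.4.2.6: 0.3% is severe pain or severe induration alone; 0.6% is their sum; 1.75% is the 1 child of 57 with severe limb pain; 1.0% is an assumed intermediate value. Severe fever, 2.1%, stands in for fever above 40 °C.
- Jet-arm rate: 10%, assumed. The protocol gives no such rate. The infant study in 9.4.3 supports only a direction: fever of unstated height in 17/49 intradermal against 10/52 subcutaneous (two-sided Fisher p = 0.11), and local reactions that were small and slight.

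**4. Probability that no numeric rule fires (exact binomial).** Severe local reaction is treated as one composite. Phase I passes if the jet-minus-control excess is below 4 (the strictest local limit in 10.10) and the pooled count is below 5 of 48. Phase II passes if the sum of Bin(134, 0.10) and two Bin(134, b) counts is below 20. The joint probability is the product.

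| Other arms, b | Phase I passes | Phase II below 20 | Joint | Joint with excess limit 5 |
|---|---|---|---|---|
| 0.3% | 0.931 | 0.925 | 0.861 | 0.905 |
| 0.6% | 0.929 | 0.885 | 0.823 | 0.860 |
| 1.0% | 0.925 | 0.816 | 0.755 | 0.785 |
| 1.75% | 0.911 | 0.646 | 0.589 | 0.607 |

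The by-arm gate alone (excess below 4 of 16) passes 10% v 0.6% with probability 0.94. For fever at 10% v 2.1% it passes with probability 0.95, after which no phase II count applies unless the fever is serious.

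**5. Where the pooled rule does work.** Probability that the phase II local count reaches 20:

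| Other arms | Jet 10% | 12% | 15% | 20% |
|---|---|---|---|---|
| 0.6% | 0.115 | 0.315 | 0.688 | 0.973 |
| 1.75% | 0.354 | 0.604 | 0.874 | 0.993 |

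**6. What by-arm looks would add.** One third of 402 is 134 children, about 45 per arm; two thirds is 268, about 89 per arm. Each range runs from dose-1 data only (taken as half the risk) to full two-dose data.

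| Excess seen | 45 per arm | 89 per arm |
|---|---|---|
| Local ≥5, 10% v 0.6% | 0.07–0.43 | 0.42–0.91 |
| Local ≥5, 10% v 1.75% | 0.06–0.34 | 0.34–0.82 |
| Fever ≥4, 10% v 2.1% | 0.14–0.49 | 0.48–0.87 |

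**7. False alarms.** With equal rates in all arms, over two investigational arms and two looks (simulation): fever ≥4 at 2.1%, about 7%; local ≥5, 0.03% at 0.6% and 1.2% at 1.75%.

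**The case against.** The strongest reply is that blinding hides the arm but not the frequency. With 10% in the jet arm and 0.6% elsewhere, phase II would yield about 134 × 0.10 + 268 × 0.006 = 15.0 severe local events, against 402 × 0.006 = 2.4 at background, roughly six-fold. For fever the figures are about 19.0 against 8.4. Investigators could notice this, and 10.5.2.2.1 with 10.12 gives them a route to the DSMB, which holds the codes and may meet for cause. There are also progress reports to both IRBs (7.1), and the four meetings are a minimum. No document supports a 10% severe rate; the vaccine is given at 40% of the standard antigen (3 v 7.5 µg); and excess limits set for 16 per arm are not calibrated for 89.

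Much of this stands. It is why the probabilities above describe numeric rules not firing and do not measure review failing. But the 10.12 route depends on blinded investigators judging a pooled frequency to be unexpected. It covers only certain unanticipated non-serious events and cannot attribute an excess to an arm. The board's power to meet for cause does not help much if it need not receive the data that would show cause. The calibration point is fair and limits how the looks should be used: no automatic action should follow from them.

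**Conclusion.** The point holds. As section 10.11 reads, no DSMB review is scheduled between the end of phase I and the completion of phase II. The 10.9.2 counts are pooled, and non-serious fever above 40 °C counts toward neither. For expected, non-serious reactions at a moderate excess in the jet arm, a by-arm tally before phase II ends is left to discretion.

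The size depends on assumed rates. At 10% in the jet arm, the chance that no numeric rule fires is 0.86 to 0.59 as the background in each other arm goes from 0.3% to 1.75%. At about 15% or more the pooled rule would probably bring an unblinded review, so the gap concerns excesses below that. Section 8.8, to which 10.11 refers for the DSMB, was not available and is not judged. This is a worthwhile improvement to safety oversight; the partial safeguards keep it from being a fatal defect.

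**What to change.** Amend 10.11 and 10.9.2 so that, when about one third and two thirds of phase II children have completed the day 7 visit after dose 1, the investigators send the existing DSMB all phase II adverse-event data accrued to date, for both doses, listed by study ID. The board links its codes, repeats the 10.10 by-arm tally including fever above 40 °C, and advises under its existing powers, weighing any excess by judgement. Keep the pooled counts in 10.9.2 as immediate triggers.

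The cost is protocol wording, one or two listings and one or two conference calls. No new staff, procedures or participants are needed, and the investigators stay blinded. The downside is the fever false-alarm chance of about 7% at the 10.10 limit, before the other criteria are added; with no automatic action attached, the board can absorb it. The first look has limited sensitivity, so most of the gain comes from the second.
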